#### 11.6 Data and Safety Monitoring Committee Oversight

A Data and Safety Monitoring Committee will oversee the conduct of the study. The Committee consists of four members from outside of SWOG, 3 SWOG members, 3 non-voting representatives from the National Cancer Institute (NCI), and the Group Statistician (non-voting). The members of this Committee will receive confidential reports every 6 months from SWOG Statistical Center, and will meet at the Group's bi-annual meetings as necessary. The Committee will be responsible for decisions regarding possible termination and/or early reporting of the study.

### 12.0 DISCIPLINE REVIEW

There will be no formal discipline review done in conjunction with this study.

### 13.0 REGISTRATION GUIDELINES

#### 13.1 Registration Timing

Patients must be registered prior to initiation of treatment (no more than ten working days prior to planned start of treatment).

#### 13.2 Investigator/Site Requirements

This study is supported by the NCI Cancer Trials Support Unit (CTSU).

Prior to the recruitment of a patient for this study, investigators must be registered members of a Cooperative Group. Each investigator must have an NCI investigator number and must maintain an "active" investigator registration status through the annual submission of a complete investigator registration packet (FDA Form 1572 with original signature, current CV, Supplemental Investigator Data Form with signature and Financial Disclosure Form with original signature) to the Pharmaceutical Management Branch, CTEP, DCTD, NCI. These forms are available on the CTSU Web site ([http://ctep.cancer.gov/investigatorResources/investigator\\_registration.htm](http://ctep.cancer.gov/investigatorResources/investigator_registration.htm)). Questions should be directed to the CTEP Investigator Registration Help Desk by e-mail at [[contact]](mailto:[contact]).

Each investigator or group of investigators at a clinic site must obtain IRB approval for this protocol and submit IRB approval and supporting documentation to the CTSU Regulatory Office before they can enroll patients. Study centers can check the status of their registration packets by querying the Regulatory Support System (RSS) site registration status page of the CTSU member web site by entering credentials at <https://www.ctsu.org>.

Requirements for site registration:

- CTSU IRB Certification
- CTSU IRB/Regulatory Approval Transmittal Sheet

Note: Sites participating on the NCI CIRB initiative and accepting CIRB approval for the study are not required to submit separate IRB approval documentation to the CTSU Regulatory Office for initial, continuing or amendment review. This information will be provided to the CTSU Regulatory Office from the CIRB at the time the site's Signatory Institution accepts the CIRB approval. The Signatory site may be contacted by the CTSU Regulatory Office or asked to complete information verifying the participating institutions on the study. Other site registration requirements (i.e., laboratory certifications, protocol-specific training certifications, or modality credentialing) must be submitted to the CTSU Regulatory Office or compliance communicated per protocol instructions.

### 13.3 OPEN Registration Requirements

The individual registering the patient must have completed the appropriate SWOG Registration Worksheet. The completed form must be referred to during the registration but should not be submitted as part of the patient data.

Oncology Patient Enrollment Network (OPEN) will also ask additional questions that are not present on the SWOG Registration Worksheet. The individual registering the patient must be prepared to provide answers to the following questions:

- a. Institution CTEP ID
- b. Protocol Number
- c. Registration Step
- d. Treating Investigator
- e. Cooperative Group Credit
- f. Credit Investigator
- g. Patient Initials
- h. Patient's Date of Birth
- i. Patient SSN (SSN is desired, but optional. Do not enter invalid numbers.)
- j. Country of Residence
- k. ZIP Code
- l. Gender (select one):
  - Female Gender
  - Male Gender

- m. Ethnicity (select one):
- Hispanic or Latino
  - Not Hispanic or Latino
  - Unknown
- n. Method of Payment (select one):
- Private Insurance
  - Medicare
  - Medicare and Private Insurance
  - Medicaid
  - Medicaid and Medicare
  - Military or Veterans Sponsored NOS
  - Military Sponsored (Including Champus & Tricare)
  - Veterans Sponsored
  - Self Pay (No Insurance)
  - No Means of Payment (No Insurance)
  - Other
  - Unknown
- o. Race (select all that apply):
- American Indian or Alaska Native
  - Asian
  - Black or African American
  - Native Hawaiian or other Pacific Islander
  - White
  - Unknown

#### 13.4 Registration Procedures

- a. All site staff (SWOG and CTSU Sites) will use OPEN to enroll patients to this study. OPEN is a web-based application that is integrated with the CTSU Enterprise System for regulatory and roster data and, at the time of patient registration, initializes the patient in the Rave database. OPEN can be accessed at <https://open.ctsu.org> or from the OPEN tab on the CTSU members' side of the website at <https://www.ctsu.org>, or from the OPEN Patient Registration link on the SWOG CRA Workbench.
- b. Prior to accessing OPEN site staff should verify the following:
- All eligibility criteria have been met within the protocol stated timeframes and the affirmation of eligibility on the Registration Worksheet has been signed by the registering investigator or another investigator designate. Site staff should refer to [Section 5.0](#) to verify eligibility.
  - All patients have signed an appropriate consent form and HIPAA authorization form (if applicable).
  - The study site is listed as "approved" in the CTSU RSS.
- c. Access requirements for OPEN:
- Site staff will need to be registered with CTEP and have a valid and active CTEP-IAM account. This is the same account (user ID and password) used for the CTSU members' web site. Additional information about obtaining a CTEP-IAM account can be found at

[http://ctep.cancer.gov/branches/pmb/associate\\_registration.htm](http://ctep.cancer.gov/branches/pmb/associate_registration.htm).  
Questions should be directed to the CTEP Associate Registration Help Desk by e-mail at [[contact]](mailto:[contact]).

- To perform registrations, the site must have been assigned the 'Registrar' role on the SWOG or CTSU roster:
  1. If you are a SWOG member, to perform registrations on SWOG protocols you must have an equivalent 'Registrar' role on the SWOG roster. Role assignments are handled through SWOG.
  2. If you are not a SWOG member, to perform registrations on SWOG protocols you must have the role of Registrar on the CTSU roster. Site and/or Data Administrators can manage CTSU roster roles via the new Site Roles maintenance feature under RSS on the CTSU members' web site. This will allow them to assign staff the "Registrar" role.

Note: The OPEN system will provide the site with a printable confirmation of registration and treatment information. Please print this confirmation for your records.

- d. Further instructional information is provided on the OPEN tab of the CTSU members' side of the CTSU website at <https://www.ctsu.org> or at <https://open.ctsu.org>. For any additional questions contact the CTSU Help Desk at [name] or [[contact]](mailto:[contact]).

- 13.5 Exceptions to SWOG registration policies will not be permitted.
- a. Patients must meet all eligibility requirements.
  - b. Institutions must be identified as approved for registration.
  - c. Registrations may not be cancelled.
  - d. Late registrations (after initiation of treatment) will not be accepted.

## 14.0 DATA SUBMISSION SCHEDULE

### 14.1 Data Submission Requirement

Data must be submitted according to the protocol requirements for **ALL** patients registered, whether or not assigned treatment is administered, including patients deemed to be ineligible. Patients for whom documentation is inadequate to determine eligibility will generally be deemed ineligible.

### 14.2 Master Forms

Master forms are included in [Section 18.0](#) and (with the exception of the sample consent form and the Registration Worksheet) must be submitted to the Data Operations Center in Seattle. Data from approved SWOG institutions must be submitted on-line via the Web; see [Section 14.3a](#) for details. Exceptions to online data submission are patient-completed (e.g. Quality of Life) forms and source documents (e.g. pathology/operative/lab reports).

### 14.3 Data Submission Procedures

- a. SWOG institutions must submit data electronically via the Web by using the SWOG CRA Workbench. To access the CRA Workbench, go to the SWOG Web site (<http://swog.org>) and logon to the Members Area. After you have logged on, click on the *CRA Workbench* link to access the home page for CRA Workbench website. Next, click on the *Data Submission* link and follow the instructions. For new users, the link to a "Starter Kit" of help files may be found by clicking on the **Starter Kit** link at the Members' logon page.

To submit data via the web the following must be done (in order):

1. You are entered into the SWOG Roster and issued a SWOG Roster ID Number,
2. You are associated as an investigator or CRA/RN at the institution where the patient is being treated or followed, and
3. Your Web User Administrator has added you as a web user and has given you the appropriate system permissions to submit data for that institution.

For assistance with points 1 and 2 call the Operations Office at [name]. For point 3, contact your local Web User Administrator (refer to the "Who is my Web User Administrator?" function on the [swog.org](http://swog.org) Members logon page). For other difficulties with the CRA Workbench, please email [[contact]](mailto:[contact]).

- b. If you need to submit data that are not available for online data submission, the only alternative is via facsimile. Should the need for this occur, institutions may

submit data via facsimile to [name] or [name] locally. Please do not use cover sheet for faxed data. Please make sure that each page of all faxed data include the SWOG patient number, study ID and patient initials.

- c. Data Submission Instructions for non-SWOG Institutions (CTSU): See the [CTSU participation table](#).

#### 14.4 Data Submission Overview and Timepoints

- a. WITHIN 7 DAYS OF REGISTRATION:

Submit copies of the following:

**S0931** Prestudy Form

**S0931** Tumor Specimen Processing Form (for patients who consent to the translational medicine studies)

Surgical and Radiology Reports

Pathology Report confirming renal cell carcinoma including subtypes.

- b. IF PATIENT CONSENTED:

Submit specimens within 28 days of obtaining as outlined in [Section 15.0](#).

- c. WITHIN 7 DAYS OF COMPLETION OF EACH CYCLE (EVERY SIX WEEKS) WHILE ON PROTOCOL TREATMENT:

**S0931** Treatment Form

**S0931** Adverse Event Form

- d. EVERY EIGHTEEN WEEKS FOR THE FIRST 54 WEEKS (REGARDLESS OF EARLY PROTOCOL TREATMENT DISCONTINUATION), AND THEN EVERY 6 MONTHS FOR THE FOLLOWING 2 YEARS, AND THEN ANNUALLY UNTIL 10 YEARS AFTER REGISTRATION, RECURRENCE OR DEATH WHICHEVER COMES FIRST:

**S0931** Recurrence Assessment Form

- e. WITHIN 14 DAYS OF DISCONTINUATION OF ALL PROTOCOL TREATMENT:

Off Treatment Notice

Final **S0931** Treatment Form

Final **S0931** Adverse Event Form

- f. AFTER OFF ALL PROTOCOL TREATMENT, EVERY SIX MONTHS FOR TWO YEARS AND ANNUALLY UNTIL TEN YEARS AFTER REGISTRATION OR UNTIL DEATH:

Submit copies of the **S0931** Specific Follow Up Form

- g. WITHIN 14 DAYS OF RECURRENCE:
- S0931** Adverse Event Form
- Off Treatment Notice
- If patient was off protocol treatment:
- S0931** Specific Follow-Up Form
- For all patients:
- S0931** Recurrence Assessment Form
- Radiology and pathology reports documenting recurrence.
- h. WITHIN 4 WEEKS OF KNOWLEDGE OF DEATH:
- If patient was still on protocol treatment:
- Notice of Death
- Final S0931** Treatment Form
- Final S0931** Adverse Event Form
- If patient was off protocol treatment:
- Notice of Death
- S0931** Specific Follow-Up Form

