### 1.2 Secondary Objectives

- a. To compare overall survival in those patients randomized to everolimus versus those randomized to placebo.
- b. To compare qualitative and quantitative toxicity between the two study arms.

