#### Pharmacodynamic Evaluation of Everolimus in Adjuvant Renal Carcinoma Subjects

Everolimus was originally developed for its immunosuppressant properties in the prevention of rejection after solid-organ transplantation. Chronic daily dosing of an mTOR inhibitor has not been studied in an adjuvant cancer population, and potential adverse effects of longer-term administration of everolimus need to be carefully assessed. While this trial will evaluate one year of adjuvant therapy, it is possible that longer dosing duration may eventually prove advantageous, and understanding and predicting for chronic toxicity is important in this population. We will therefore study adverse effects of everolimus in this study population and determine a relationship with steady-state trough levels of the drug.

The published literature on steady-state pharmacokinetics and chronic toxicity has largely been in the post-transplant setting in which everolimus has been co-administered with other immunosuppressant drugs as part of triple-therapy rejection prophylaxis. (36,37) The applicability of this toxicity data to the adjuvant renal carcinoma population is clouded by the potential contribution of co-administered immunosuppressant drugs and other factors peculiar to post-transplant setting. Since the adjuvant renal carcinoma setting represents a population with curative potential, mTOR inhibitor side effects with potential long-term implications are of concern, including hyperlipidemia and immunosuppression, which may be a particular issue with the daily dosing regimen studied in cancer. (38)

In renal transplantation patients, steady-state minimum concentrations were well correlated with AUC (correlation coefficient [r value] = 0.88). (39) A relationship was seen between AUC and thrombocytopenia ( $p=0.03$ ), and there was a positive trend between AUC and both hypercholesterolemia and hypertriglyceridemia. These results suggest that monitoring  $C_{min}$  may serve as a good marker for overall everolimus exposure. (40) In the post-transplantation setting, trough levels are recommended to be in the desired range of 3 to 8 ng/mL to optimize efficacy and decrease the incidence of adverse reactions, although it has been suggested that everolimus use with levels of up to 15 ng/mL is manageable. (41,42) In Phase I studies in advanced cancer patients using 10 mg daily dosing, trough levels exceeded the recommended range for the transplant population. (43,44)

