#### Most Prevalent Grade 2-4 Adverse Events in the Everolimus Arm of EVEREST

Among all Randomized Patients on the Everolimus Arm Who Received Any Study Drug

Toxicity	% of Evaluable with Grade 2-4
High Cholesterol	10%
Fatigue	19%
Hyperglycemia	14%
Hypertriglyceridemia	27%
Oral mucositis	35%
Rash	14%
Composite Endpoints	
Any Toxicity Grade 2-4	87%
Any Toxicity Grade 3-4	46%
Refusal/Tox within first 3 months	25%
Refusal/Tox within first 6 months	41%
Refusal/Tox prior to 12 months	52%

In order to simplify power calculations related to everolimus blood concentrations, we will assume the distribution of values will be divided into quartiles. The following table indicates the minimally detectable odds ratio that could be detected between the lowest and highest quartile in terms of predicting an adverse event. A range of prevalences are illustrated below to show how the effect size changes with the prevalence of the adverse event.

Minimally Detectable Odds Ratio for Highest versus Lowest Quartile of everolimus in the blood, assuming 80% Statistical Power and a Two-sided Alpha=0.05.

	Prevalence of Adverse Event Endpoint				
	10%	20%	30%	40%	50%

Q4 vs. Q1 of everolimus concentration	6.5	3.6	3.0	2.7	2.7
---------------------------------------	-----	-----	-----	-----	-----

An individual adverse event that is only reported by 10% of patients who receive everolimus will need to have a very strong association with concentration of everolimus in the blood (odds ratio 6.5 between highest and lowest concentration) in order to be detected as a significant association. An association of any Grade 3-4 toxicity only needs to be in the range of an odds ratio of 2.7 to be detectable.

For patients who have had a dose reduction of protocol therapy at the time of their blood draw, we will handle this in two ways. First, we will just analyze the everolimus level as it appears in the blood and ignore the dose received, and the second approach will standardize the amount of everolimus in the blood conditional on the dose of drug taken.

Logistic regression will be used to model adverse event outcomes with everolimus blood concentration as a predictor, adjusting for other stratification factors and age, gender and race.

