
NOTE: Protocol specific exceptions to expedited reporting of serious adverse events are found in the Specific Protocol Exceptions to Expedited Reporting (SPEER) portion of the CAEPR or [Section 16.1f.]
 
Expedited AE reporting timelines are defined as:
 
 
o “24-Hour; 5 Calendar Days” - The AE must initially be reported via CTEP-AERS within 24 hours of learning of the AE, followed by a complete expedited report within 5 calendar days of the initial 24-hour report.
 
o “10 Calendar Days” - A complete expedited report on the AE must be submitted within 10 calendar days of learning of the AE.
 
				

Serious adverse events that occur more than 30 days after the last administration of investigational agent/intervention and have an attribution of possible, probable, or definite require reporting as follows:
 
Expedited 24-hour notification followed by complete report within 5 calendar days for:
 
 
• All Grade 4, and Grade 5 AEs
 
 
Expedited 10 calendar day reports for:
 
 
• Grade 2 adverse events resulting in hospitalization or prolongation of hospitalization
 
• Grade 3 adverse events
 
				

May 5, 2011
				

f. **Additional Instructions or Exceptions to CTEP-AERS Expedited Reporting Requirements for Late Phase 2 and Phase 3 Trials Utilizing an Agent under a Non-CTEP IND:**

1) **Group-specific instructions.**

Supporting Documentation Submission - Within **5 calendar days** submit the following to the SWOG Operations Office by fax to [contact] or mail to the address below:

- Printed copy of the first page of the CTEP-AERS report
- Copies of clinical source documentation of the event
- If applicable, and they have not yet been submitted to the SWOG Data Operations Center, copies of Off Treatment Notice and/or Notice of Death.

2) The adverse event listed below does not require expedited reporting via CTEP-AERS:

- Grade 4 myelosuppression

g. **Reporting of Secondary Malignancy Including AML/ALL/MDS**

1. A secondary malignancy is a cancer caused by treatment for a previous malignancy (e.g., treatment with investigational agent/intervention, radiation or chemotherapy). A secondary malignancy is not considered a metastasis of the initial neoplasm.

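### Routine adverse event forms stop soon after treatment ends, and Section 11.3 compares toxicity without regard to time at risk, so crude proportions may understate late or background events on everolimus

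*Combined protocol and SAP*

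**What the plan says.** **Objective.** Section 1.2b: "To compare qualitative and quantitative toxicity between the two study arms". Section 2.0 adds that, in a population that may be cured, "mTOR inhibitor side effects with potential long-term implications are of concern, including hyperlipidemia and immunosuppression".

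**Routine collection (Section 14.4).** The Adverse Event Form is due:
- each cycle: "WITHIN 7 DAYS OF COMPLETION OF EACH CYCLE (EVERY SIX WEEKS) WHILE ON PROTOCOL TREATMENT" (14.4c);
- as a final form: "WITHIN 14 DAYS OF DISCONTINUATION OF ALL PROTOCOL TREATMENT" (14.4e);
- at recurrence: "WITHIN 14 DAYS OF RECURRENCE" (14.4g), where it stands above the line for patients already off treatment and so is not limited to those on drug;
- at death, only if the patient was still on treatment (14.4h).

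After treatment, the schedule "AFTER OFF ALL PROTOCOL TREATMENT, EVERY SIX MONTHS FOR TWO YEARS AND ANNUALLY UNTIL TEN YEARS AFTER REGISTRATION OR UNTIL DEATH" (14.4f) lists only the Specific Follow Up Form, whose content is not in the text supplied. In the Section 9.0 calendar, as extracted, the toxicity row is marked in treatment cycles and in no off-treatment column. Recurrence assessment, by contrast, continues on the Year 1 schedule whether or not the patient has stopped drug early.

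**Expedited reporting (Section 16.1).** Table 16.1 covers serious events to 30 days after the last dose. Its footnote extends this to "Serious adverse events that occur more than 30 days after the last administration of investigational agent/intervention" if they are at least possibly attributed to treatment, within stated grades.

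**Analysis (Section 11.3).** The arms are to be compared on adverse events, with toxicity rates estimated to within ±3.7% at 732 per arm. No observation window, time-at-risk summary, exposure adjustment or time-to-event method is stated.

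**Stopping (Section 11.5).** The everolimus-arm table gives refusal or toxicity stops of 25% by 3 months, 41% by 6 months and, in the row "Refusal/Tox prior to 12 months", 52%. No placebo figure appears.

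**The concern.** A proportion with an event depends on how long patients are watched. Here routine watching is tied to treatment, and at least half of the everolimus arm leaves treatment early. If the placebo arm stays on longer, an event that arises at the same rate in both arms will be recorded less often on everolimus, simply because there was less time in which to record it.

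The sponsor already regards early stopping as large enough to matter: the July 2015 revision in Section 11.1 changed the effective hazard ratio and the sample size because of it. Section 11.3 makes no matching allowance for toxicity. What is at stake is a stated secondary comparison and the safety half of the study hypothesis in Section 2.0, that everolimus improves recurrence-free survival without excessive toxicity.

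**Working it through.** **1. The plan's own figures.**
- Precision for one arm at p = 0.5: 1.96 × √(0.25/732) = 3.62%. With a continuity correction of 1/(2 × 732) it is 3.69%, which rounds to the stated 3.7%.
- The stopping figures fit the July 2015 revision. With 59% past 6 months at full benefit and 41% − 25% = 16% at half benefit, exp[(0.59 + 0.5 × 0.16) × ln 0.75] = 0.825, against the stated 0.82.

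**2. Time on drug, everolimus.** The proportions on drug at 0, 3, 6 and 12 months are 1, 0.75, 0.59 and 0.48. Joined by straight lines:

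3 × 0.875 + 3 × 0.67 + 6 × 0.535 = 7.845 months, or 65% of 12 months.

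If all stops fall at the start of each interval the mean is 6.9 months; if all fall at the end, 8.8.

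**3. Time on drug, placebo (assumption).** With 5% to 30% stopping evenly over the year, the mean is 12 × (1 − 0.05/2) = 11.7 to 12 × (1 − 0.30/2) = 10.2 months. The ratio of everolimus to placebo is 0.67 to 0.77.

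**4. Effect on a crude proportion.** Take an event with the same constant hazard in both arms, independent of stopping. The recorded proportion is ∫ λe^(−λt) S(t) dt over 12 months, with S(t) the proportion still on drug. For a true 12-month risk of 20%, λ = −ln(0.8)/12 = 0.0186 per month. Events then arise in 5.43%, 5.13% and 9.44% of patients in months 0–3, 3–6 and 6–12. Multiplying by the mean on-drug proportions gives, for everolimus,

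5.43 × 0.875 + 5.13 × 0.67 + 9.44 × 0.535 = 13.2%; the exact integral is 13.3%.

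| True risk, both arms | Recorded, everolimus | Recorded, placebo (5% to 30% stop) | Spurious gap, points |
|---|---|---|---|
| 10% | 6.6% | 9.8% to 8.5% | −3.2 to −1.9 |
| 20% | 13.3% | 19.5% to 17.1% | −6.3 to −3.9 |
| 40% | 27.0% | 39.1% to 34.5% | −12.1 to −7.5 |

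For scale, the 95% half-width for a difference between arms near 20% is 1.96 × √(2 × 0.16/732) = 4.1 points.

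**5. Sensitivity.**
- *Thirty more days of observation after the last dose, both arms:* the 20% row becomes −5.5 to −3.5 points. This helps, but does not equalise the arms.
- *Recurrence also ends treatment.* Multiplying both on-drug curves by e^(−0.1027t), t in years, the placebo hazard in the December 2020 update, gives 12.7% against 18.6% to 16.3%, a gap of −5.9 to −3.6 points.
- *Placebo stopping as high as 52%, spread evenly:* 13.3% against 15.0%, a gap of −1.7 points.
- *Early toxicity:* with a true 35% incidence and exponential onset of mean 1.5 to 3 months, 31% to 28% is still recorded on everolimus even if stopping is unrelated to the event.

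**The case against.** Several stronger readings are tempting, and the documents do not support them.

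- **That adverse events are collected only while the patient takes drug.** The final form, the form at recurrence and Table 16.1 with its footnote all reach beyond the last dose, and the Specific Follow Up Form might carry toxicity items. What remains uncovered, as far as is shown, is the routine recording of non-serious events between the final form and recurrence. Serious events beyond 30 days are reportable only if attributed.
- **That the comparison is known to favour everolimus.** The stopping table covers everolimus alone. Less stopping on placebo is plausible but undocumented, so the direction is conditional.
- **That toxicity in general is lost.** Toxicity that causes stopping is seen before or at stopping, and with an elimination half-life of about 30 hours (Section 3.1) much new drug toxicity long after the last dose is not an obvious expectation. The model in the working describes background, cumulative or late events and assumes that stopping is independent of them.
- **That Section 2.0 promises surveillance after treatment.** Its call for careful assessment concerns longer-term dosing, which the per-cycle forms do observe.

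It can also be said that on-treatment toxicity is a coherent estimand, and that collection off drug to week 54 would add largely unexposed time. Both are fair. But an on-treatment estimand still needs a stated window and a measure that allows for different time on treatment, and Section 11.3 gives neither. Nothing there forbids such a summary; nothing provides for it.

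**Conclusion.** The point holds in a limited form. Routine recording ends soon after treatment stops, apart from the form at recurrence. The planned comparison ignores time at risk, and everolimus patients average about 65% of a year on drug. If 5% to 30% of placebo patients stop within the year, crude proportions for an event with a true 20% risk in both arms would differ spuriously by about 4 to 6 points in favour of everolimus. That is about as large as the sampling error of the difference, or larger.

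The figure rests on an assumed placebo rate, a constant and equal event hazard, stopping unrelated to the event, straight lines between the three published stopping figures, and follow-up forms that add no toxicity data. It shrinks for early drug-related toxicity and as placebo stopping approaches that on everolimus. The sponsor holds the placebo rate and can settle the direction. This is worth changing because it improves a stated secondary comparison at little cost; it is no evidence that the toxicity results are wrong.

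**What to change.** **Section 11.3 (main change, from data already held).**
- State the observation window for the toxicity comparison.
- Report time at risk and stopping rates by arm, with reasons for stopping.
- Beside the crude proportions, give time to first Grade 3 or higher event as cumulative incidence, or rates per patient-month. Treat the end of adverse event observation as censoring: counting treatment stop as a competing event would largely return the crude proportion. The six-week forms place onset at least within a cycle.
- Say that toxicity-driven stopping makes this censoring informative, and that rates per patient-month assume a roughly constant hazard; hence both presentations.

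**Section 14.4 and the Section 9.0 calendar (where collection is still possible).** Carry the Adverse Event Form to 30 days after the last dose in both arms, to match Table 16.1. The December 2020 update puts the final analysis at March 2022 after six years of follow-up from last accrual, so accrual ended around 2016 and treatment around 2017. For this trial the form change probably comes too late.

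Collection off drug to week 54, at Year 1 visits already required, is optional, since it changes the estimand.

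**Cost.** One extra summary table and, if forms are extended, a little more data entry.
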